7.1 DEMOGRAPHIC AND OTHER BASELINE CHARACTERISTICS

7.1.1 Disposition of patients

For patient disposition the standard descriptive table will be populated. Additionally, patients with discontinuations by initial treatment and the reasons will be listed.

7.1.2 Important protocol violations

A listing with the number of patients with protocol violations by initial treatment will be created in Section 15 of the CTR.

7.1.3 Demographic and other baseline

Standard descriptive analysis and summary tables for all patients treated by initial treatment will be created for demography, smoking/alcohol status, previous therapies, physical

examination, disease evaluation at baseline, virology screening, ECOG and oncological history.

7.2 CONCOMITANT DISEASES AND MEDICATION

Only descriptive statistics are planned for this section of the report.

Concomitant therapies will be coded according to World Health Organisation Drug Dictionary (WHO DD). Concomitant therapies (CTh) will be classified according to the Anatomical, Therapeutic, Chemical (ATC) classification system. The third ATC level will be used to categorise CThs by therapy type. In situations where a medical product may be used for more than one equally important indication, there are often several classification alternatives. As appropriate, patients receiving CThs with more than one possible ATC level-three category will be counted more than once; footnotes will clarify this possible double counting in tables.

A summary of the most frequently used concomitant medications (drug classes and generic name) during the treatment and before starting of treatment will be reported. Separate listings/tables will be provided for therapy starting before therapy and those therapies starting after first administration of the trial drug as well as for therapies with missing or incomplete start dates. A summary of concomitant therapy will be given.

Listings of the data will present the concomitant therapy PT and verbatim text as well as the verbatim text of the indication. In addition the listings will include study day for start and stop dates and duration of therapy. Patients with no concomitant therapy will not be included in the listing.

7.3 TREATMENT COMPLIANCE

Compliance will be evaluated by whether or not the medication was always administered according to protocol for BI 836826.

The numbers of patients complying with the administration of trial medication according to protocol (yes/no) will be listed.

For patients with administration "not according to the protocol" a listing with comments will be presented.

Furthermore, a listing will show all administrations of trial drug including also the administration of premedication acetaminophen/paracetamol, antihistamine and glucocorticoid.

7.4 PRIMARY ENDPOINTS

The primary endpoints of this trial are the MTD and the number of DLTs during the MTD evaluation period. The MTD is determined from the occurrences of DLTs during the MTD evaluation period, which is from treatment start until the second infusion of BI 836826 plus 7 days. An overall summary of the DLTs (see CTP Section 5.2.1.1 for definitions of DLT)

which occurred during the MTD evaluation period will be provided for each dose cohort. Patients, if any, who did not complete at least two administrations of BI 836826 for reasons other than DLT will be excluded from the analysis of the primary endpoint. These patients will be replaced at the same dose level.

At the end of the dose escalation phase, a brief interim safety analysis was performed and reported to further describe the dose escalation steps actually occurred and to justify the determination of MTD, see also [Section 9.1](#) and “CTR – Phase I Safety Analysis Report” ([8](#)).

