### 3. DESCRIPTION OF DESIGN AND TRIAL POPULATION

#### 3.1 OVERALL TRIAL DESIGN AND PLAN

The trial is an open-label, non-randomized phase I dose-escalation trial with modified 3+3 design to evaluate the tolerability and safety of BI 836826, and to determine the MTD or to establish the recommended dose for further development.

Single patient cohorts will be treated until a drug-related adverse event of CTCAE grade 2 or higher occurs during the first two weeks of the first treatment course, *i.e.* from first infusion to 7 days after the second infusion. When this occurs the single patient cohort and all subsequent cohorts will be expanded to three patients, following a fixed dose-escalation design with dose de-escalation steps ([R04-0569](#)), *i.e.* the single patient cohort will be expanded with 2 additional patients to 3 patients in total. When one patient of the cohort of three patients experiences a dose limiting toxicity (DLT) (for definition see [5.2.1.1](#)), three additional patients will be treated at the same dose level according to a standard 3+3 design. If none of the three additional patients experiences a DLT, then the dose-escalation will be continued by treating the next cohort of three patients at the next higher dose level. If at least two out of up to six patients at a dose level experience a DLT, the MTD has been exceeded and the dose will be de-escalated until a dose level is reached in which at most one DLT out of six patients is observed ([R01-0028](#)). At the MTD, no more than one patient out of six patients may experience DLT, *i.e.* the MTD is defined as the highest dose studied for which the incidence of dose-limiting toxicity is no more than 17% during the first 2 weeks of the first course.

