#### 4.1.4.3 Management of infections:

During treatment with BI 836826 patients need to be carefully monitored for infections at each clinic visit. Frequent blood counts monitoring will help to identify patients with prolonged neutropenia who might be at risk for severe infections. It is highly recommended that the treatment of infection starts immediately upon very first clinical symptoms. Depending on investigators' assessment the use of growth factors, antibiotics, antifungals, and antivirals should be considered, and implemented with no delay. The next administration of BI 836826 needs to be delayed until the patient has cleared an infection and has recovered from neutropenia as outlined in sec: 4.1.4.4

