#### **5.2.1.1 Dose limiting toxicity**

Dose limiting toxicity (DLT) is defined as any drug-related non-haematological adverse event CTCAE grade 3 or higher, except infusion-related reactions associated with the administration of BI 836826.

Complications resulting from haematological adverse events, e.g. bleeding due to thrombocytopenia or infection due to neutropenia are classified as non-haematological adverse events and are covered by the above definition of DLT. Nevertheless, haematological adverse events, e.g. neutropenia, thrombocytopenia and anemia will be considered for definition of the dose for further development.

The MTD will be defined on the basis of DLT observed during the first 2 weeks of the first treatment course. In case of a delay of the second administration, evaluation of DLT should be prolonged to 7 days after the second administration. However, for those patients who receive more than two doses of BI 836826, all adverse events corresponding to the above definition of DLT will be considered for the purpose of confirming the MTD and for the selection of the recommended dose for treatment of the expansion cohort and for further development. In regular intervals, all available safety data including adverse events qualifying for DLT will be submitted to the DSMB. The DSMB will independently assess this information and provide recommendations for trial conduct and dose-escalation.

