### 7.3 PLANNED ANALYSES

#### 7.3.1 Primary analyses

The primary objective for this study is the tolerability and safety of BI 836826 as reflected by the MTD (for a definition of MTD, please refer to [section 3.1](#) and [section 5.2.1.1](#)). In order to identify the MTD, the number of DLTs during the first two weeks of the first course at each dose level must be presented. For the analysis of tolerability and safety, please refer to [section 7.3.3](#). If an MTD is not reached, an OBD can be determined from available data on safety and pharmacodynamic analyses, B cell depletion and reduction in tumour size (see sections [2.2](#) and [3.1](#)).

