5. ENDPOINTS

5.1 PRIMARY ENDPOINTS

The primary endpoints of this trial are the MTD and the number of dose limiting toxicities (DLTs) during the MTD evaluation period. Instead of the MTD, an OBD might be defined instead.

Maximum tolerated dose (MTD):

MTD is defined as the highest dose studied for which the incidence of DLTs is no more than 17% (i.e., 1/6 patients) during the MTD evaluation period.

The MTD evaluation period is defined as the time from the first administration of study medication to 7 days after the second administration.

Note that in case of administration of split dose during course 1, both infusions on consecutive Days 1 and 2 of Course 1 are considered as the first administration.

Additionally, all information, including adverse events (AEs) qualifying for a DLT from later times, will be considered in the final determination of the dose recommended for Phase II.

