6. GENERAL ANALYSIS DEFINITIONS

6.1 TREATMENTS

In this Phase I trial, treatments are not randomised (open-label, dose escalation). Different dose levels of BI 836826 can arise. The data will be presented for all dose cohorts separately, where Korean patients will be presented as a separate dose cohort from Caucasian patients.

In addition, the results for all patients in total, all Caucasian patients in total, and all Korean patients in total will be presented.

To justify the MTD determination, DLTs occurring during the MTD evaluation period (very first infusion of BI 836826 until the day of second infusion in Course 1 + seven days) will be presented separately from those occurring during the complete on-treatment period.

“Analysing treatment” will be used for reporting of treatment emergent AEs and to differentiate between screening, on-treatment and post-study safety data. The inequalities start date \leq onset date of AE $<$ end date will determine whether the AE will be assigned to the “analysing treatment” or not.

For the on-treatment period and the MTD evaluation period, the initial trial medication assigned at the beginning of the first treatment course will be used as the label of the analysing treatment.

AEs that have an onset date during the screening or post-study periods will be displayed in separate listings from those occurred during the on-treatment period.

The actual planned dose of trial medication administered on the day each AE started will also be derived. This will be presented in patient listings, but will not be used for defining treatments for analysis.

Labels of each analysing treatment period, analysis numbers, the labels used for display in the tables and listings in the CTR, as well as codes, decodes, sort order and labels for each trial medication used in this trial are provided in the TSAP technical document “ADS Plan”.

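### SAP 7.4 removes a patient from the primary DLT count by the recorded reason for missing infusion 2, not by whether a DLT occurred

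*SAP*

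**What the plan says.** SAP 7.4 makes the number of DLTs in the MTD evaluation period a primary endpoint, alongside the MTD. It also sets an exclusion rule for patients: those that "did not complete at least two administrations of BI 836826 for reasons other than DLT will be excluded from the analysis of the primary endpoint", and they are replaced at the same dose level.

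Protocol 5.2.1.1 defines a DLT by drug-relatedness, non-haematological type and CTCAE grade (3 or higher), leaving out infusion-related reactions. Why dosing stopped plays no part in that definition.

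Protocol 3.3.4.1 replaces patients with fewer than two administrations, but not those who end treatment because of a DLT. It does not address a patient who had a DLT and stopped for another reason.

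On the window, SAP 5.1 says: "The MTD evaluation period is defined as the time from the first administration of study medication to 7 days after the second administration". SAP 6.1 gives it as "very first infusion of BI 836826 until the day of second infusion in Course 1 + seven days", and SAP 7.4 agrees. The protocol's base window is a fixed one. Section 5.2.1.1 says "The MTD will be defined on the basis of DLT observed during the first 2 weeks of the first treatment course" and prolongs this only when the second administration is delayed. Section 3.1 sets the limit as "the incidence of dose-limiting toxicity is no more than 17% during the first 2 weeks of the first course", and section 7.3.1 requires that "the number of DLTs during the first two weeks of the first course at each dose level must be presented".

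SAP 7.8.1.1 also summarises patients with a DLT in the MTD evaluation period, with no exclusion stated. SAP 6.3 assigns all safety analyses to the treated set.

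**The concern.** The primary endpoint is a count of patients with an event, so whether a patient enters the count should depend on the event. Under SAP 7.4 it depends on a recorded reason that can differ from the event. A patient can have a DLT by the protocol's definition and still be recorded as missing infusion 2 for something else. That patient leaves the primary count and is replaced. The same event can then be absent from the 7.4 summary and present in the 7.8.1.1 summary of the same period.

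The trial's own safety signal makes the distinction worth settling. SAP 3 reports infections with Grade 4 neutropenia in three of four Korean patients at 100 mg. Neutropenia alone is not a DLT, but Protocol 5.2.1.1 says that "bleeding due to thrombocytopenia or infection due to neutropenia are classified as non-haematological adverse events", so the resulting infection can be one. Both can hold up infusion 2: "The next administration of BI 836826 needs to be delayed until the patient has cleared an infection and has recovered from neutropenia". Which of the two is entered as the reason then decides whether the patient counts.

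What remains to be estimated is the Korean MTD, from 3 to 6 patients at each of 50 mg and 75 mg. In cohorts of that size one patient can move the reported count across the limit.

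**Working it through.** **1. The plan's own figure.** SAP 5.1 sets the limit at 17%, given as one patient in six. 1/6 = 16.7%, which rounds to 17%. The figure reproduces.

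**2. The rule applied literally to patients with fewer than two administrations.**

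| DLT in first two weeks? | Recorded reason infusion 2 was missed | SAP 7.4 | SAP 7.8.1.1 on the treated set |
|---|---|---|---|
| Yes | The DLT | Kept | Counted |
| Yes | Progression, withdrawal, neutropenia, or Grade 4 infusion-related reaction | Excluded and replaced | Could be counted |
| No | Any reason other than DLT | Excluded and replaced | No event to count |

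Only the second row is at fault. Each reason in it is supported by the protocol: progression and withdrawal of consent (3.3.4.1), the neutrophil criterion for further dosing (4.1.4.4), and the bar on re-exposure after a Grade 4 infusion-related reaction (4.1.4.2), which is itself outside the DLT definition.

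**3. Effect of one such patient on the reported count.** Assume one other DLT in the cohort and a replacement patient without a DLT.

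- Excluded and replaced: 1/6 = 16.7%, within the limit.
- Counted among six: 2/6 = 33.3%, above the limit.
- Counted, with the replacement also in the denominator: 2/7 = 28.6%, above the limit.

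If this patient has the only DLT among the first three, the reported count is 1/3 when counted and 0/3 when excluded and replaced.

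**4. The window.** Infusion 2 is planned for day 8, and Protocol 6.1 allows a postponement of up to 3 weeks.

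- On time: 8 + 7 = day 15.
- Longest postponement: 8 + 21 = day 29, and 29 + 7 = day 36.
- Never given: the SAP wording yields no end date. The protocol's two weeks still apply, because they do not depend on infusion 2.

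**5. Illustration only.** Let p be the true DLT probability and f the share of DLT patients who fall in the second row of the table. The documents give neither. Among patients who are not excluded, the DLT rate is r = p(1 − f)/(1 − pf). The chance that the counts satisfy the 3+3 rule at one dose is (1 − r)³ + 3r(1 − r)⁵.

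| p | f = 0 (all counted) | f = 0.10 | f = 0.25 | f = 0.50 |
|---|---|---|---|---|
| 0.20 | 0.709 | 0.744 | 0.798 | 0.887 |
| 0.30 | 0.494 | 0.539 | 0.614 | 0.759 |
| 0.40 | 0.309 | 0.351 | 0.428 | 0.600 |

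For example, p = 0.30 and f = 0.25 give r = 0.225/0.925 = 0.243 and a chance of 0.614. The table shows the direction of the error. Its size depends wholly on f.

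**The case against.** The strongest reply is that the SAP follows the protocol. Protocol 3.3.4.1 exempts from replacement only those who stop because of a DLT, so the reason test is inherited. That stands, and it rules out a charge that the SAP departs from an event-based protocol rule. It does not cure the problem: the protocol passage concerns replacement, and the SAP carries the same test into exclusion from the primary analysis.

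Second, the infection example mostly resolves the other way. A drug-related Grade 3 infection is a DLT. Protocol 4.1.4.4 stops dosing for a DLT, and 3.3.4.1 ends it if recovery is insufficient. When the DLT is why infusion 2 was missed, SAP 7.4 keeps the patient. This stands too, and it leaves only cases with a different recorded reason.

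Third, the event would not be hidden. It would appear in AE outputs, in the analysis of DLTs over the whole on-treatment period, in the list of replaced patients due before database lock (SAP 6.3) and in DSMB review. SAP 5.1 also considers later DLTs for the Phase II dose. All of this is correct and lowers the weight of the point. None of these outputs says whether the patient belongs in the count compared with 1/6.

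Fourth, the missing end date is largely detail that the protocol supplies. The SAP assumes familiarity with the protocol, and Protocol 3.1 itself equates the first two weeks with the time to 7 days after the second infusion when it sets the cohort-expansion trigger. This stands, so the end date is only a supporting clarification.

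**Conclusion.** The point holds as a minor one. SAP 7.4, followed literally, drops a protocol-defined DLT when infusion 2 was missed for another recorded reason, and SAP 7.8.1.1 could count the same event. One such patient can change the reported result from 2/6 to 1/6. This assumes that such a patient occurs, which no document reports, and that the rule is applied as written. The MTD for Caucasian patients has already been reported, so the effect is confined to the Korean 50 mg and 75 mg cohorts.

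A reader might infer more, and the documents do not support it:

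- **That a late infection is wrongly lost.** If infusion 2 is never given, an event on day 18, for instance, lies outside the protocol's two-week base window. Leaving it out of the primary count follows the protocol and is not an understatement.
- **That the rule would drive escalation to 75 mg.** Escalation rests on review of all available data with a DSMB recommendation (Protocol 3.1 and 4.1.3). SAP 7.8 describes its MTD tables as documenting that selection.
- **That the loss falls mainly on patients too ill to resume.** Those stopped by the DLT itself are kept.
- **That the bias has a known size.** The pass probabilities rest on assumed values of p and f.

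**What to change.** In SAP 7.4, exclude only patients who received fewer than two administrations and had no protocol-defined DLT in the MTD evaluation period. Count every patient with such a DLT, whatever the reason infusion 2 was missed. Use the same denominator in 7.8.1.1, and state whether a replacement for a counted patient is included in it (2/6 or 2/7 in the example above).

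As a supporting clarification, state in SAP 5.1, 6.1 and 7.4 that the protocol's two-week window applies to patients who never receive infusion 2. Do not extend it to day 36, because that would lengthen the protocol's window through the SAP. Later DLTs in these patients stay in the on-treatment DLT presentation already planned.

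The DLT definition, the rules for holding doses and the 1/6 limit are unchanged. The cost is a few sentences of SAP text settled before database lock, with no new data and no change to conduct. The downside is that a DLT which would have dropped out is now counted, so a dose may appear less well tolerated than under the present wording.

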7.5 SECONDARY ENDPOINTS

7.5.1 Key secondary endpoint

Not applicable.

7.5.2 Secondary endpoints

Tumour size of target lesions, spleen nodules and liver nodules (from imaging data) will be analysed in terms of their SPD best percentage change from baseline. Summary statistics will be presented for all cohorts. A waterfall plot will also be generated to summarise tumour size reduction graphically for the SPD of the indicator lesions identified at baseline imaging. Furthermore, the tumour size of indicator lesions, liver nodules and spleen nodules and the change with respect to baseline will be listed by time point (for imaging data as well as for data from physical assessment).

Best overall response will be analysed descriptively. Frequency distributions and other descriptive statistical measures will be used to examine this endpoint. The number of patients that have either CR, CRu or PR as best overall response will be tabulated separately (to determine the remission rate, the rate of patients that have either CR, CRu or PR as best overall response).

PFS and FFS will be analysed exploratory using Kaplan-Meier methods.

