Administration of the trial drug has to be stopped temporarily in case of a DLT (see [section 5.2.1.1](#)). Patients may continue therapy only after recovery from the DLT to at least CTCAE grade 1 or pre-treatment value. The future dose of BI 836826 must be finally agreed on between the sponsor and the investigator. A reduction of the dose will be allowed only once for an individual patient during the whole trial. Treatment has to be discontinued in case the DLT is not reversible.

Intra-patient dose-escalation of BI 836826 will not be allowed in this trial.

During the dose-escalation phase, the first course (4 administrations as weekly infusions) should be given to all patients. In absence of clinical progression judged by the investigator, treatment with BI 836826 can be continued for the second course, (*i.e.* another 4 administrations) in agreement with the investigator and the clinical monitor of the sponsor. Patients with a complete or partial remission by CT scan after 8 administrations or stable disease with improvement in clinical symptoms may receive additional 4 administrations weekly as consolidation therapy after discussion between the investigator and the clinical

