### 5.1.2.2 Assessment and definition of overall best response

CT scan will be required for response assessment. CT scan will be performed at screening, at week 13 and week 25. A CT scan may be performed at end of treatment if therapy terminates earlier, *e.g.* to document progression. Bone marrow biopsy/aspirate may be performed as indicated by the investigator, but it will not be mandatory. The best response at any of CT scans done will be overall best response. Response will be assessed according to the standardized response criteria from 1999 ([R04-1585](#)).

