### 6.2.3 End of treatment and follow-up period

#### 6.2.3.1 End of treatment

The end of treatment (EOT) visit should be performed if patient and investigator refrain from further therapy at any time during the treatment period. For patients who receive course 3 (12 administrations) at the latest 8 weeks after the last administration of BI 836826. If the patient concludes the trial within a treatment course, the information required to be collected at the EOT visit should be obtained as early as possible, preferably immediately. This includes a CT scan, which may be performed if it is considered clinically indicated, *e.g.* to document disease progression. At the EOT visit assessment of all safety and efficacy parameters should be performed according to flowchart for course 3. The status of the patient at EOT has to be documented, *e.g.* in case the patient has progressive disease the date of first documentation of PD has to be recorded. The reason for the completion of active trial treatment or premature discontinuation of trial, if applicable, has to be stated together with date of last administration of the trial drug. If the patient receives other therapy for lymphoma, the therapy has to be stated by name and date of first treatment. For detail see [flowchart](#) for Course 3.

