## **7.4 HANDLING OF MISSING DATA**

No imputation will be performed on missing efficacy data. Missing baseline laboratory values will be imputed by the respective values from the screening visit. No other imputations will be performed on missing data although every effort will be made to obtain complete information on all adverse events, with particular emphasis on potential dose limiting toxicities.

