5.2.2 Other Secondary endpoints

Tumour size reduction (indicator lesions, spleen and liver nodules)

Tumour size reduction of indicator lesions, spleen nodules and liver nodules will be analysed separately as secondary endpoints as follows:

Tumour size reduction of indicator lesions will be analysed as secondary endpoint “Best % change from baseline in SPD” from imaging data.

Tumour size reduction of liver nodules will be analysed as secondary endpoint “Best % change from baseline in SPD” from imaging data.

Tumour size reduction of spleen nodules will be analysed as secondary endpoint “Best % change from baseline in SPD” from imaging data. Best overall response (according to investigator assessment):

Response will be assessed according to the Standardized or Revised Response Criteria for Malignant Lymphoma from 1999 ([[R04-1585](#)]). Each patient will be assigned to one of the

following categories:

- complete remission (CR)
- complete remission unconfirmed (CRu)
- partial remission (PR)
- stable disease (SD)
- progressive disease (PD)

Best overall response (CR, CRu, PR, SD, PD in this order) is defined as the best overall response obtained since the start of study treatment. Best overall response will be evaluated in two different ways: first, all responses as documented by the investigator (independent of the assessment procedure) will be evaluated. In a further analysis, only disease evaluations for which imaging data are available in the eCRF will be evaluated. In case PD is captured by the investigator, the response PD will be always considered as PD, independent whether imaging data is available at this timepoint or not. For both evaluations only response assessments prior to any further NHL therapy and until PD will be taken into account. For the calculation of the date of response: if patients would have their examinations contributing to the disease assessment over a number of days, the earliest date of the multiple examinations will be considered.

Progression free survival (PFS):

PFS is defined as the time from first administration of study medication until disease progression or death, whatever occurs first.

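### Best % change in SPD and the waterfall plot can show only patients with a post-baseline scan, and the visible SAP text does not account for the rest, so shrinkage is likely to look somewhat too favourable (minor)

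*SAP*

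**What the plan says.** Protocol 5.1.1 lists tumour size reduction as a secondary efficacy endpoint. SAP 5.2.2 defines it as best percentage change from baseline in SPD, from imaging, separately for indicator lesions, liver nodules and spleen nodules. SAP 7.5.2 says that these sizes "will be analysed in terms of their SPD best percentage change from baseline", with summary statistics for all cohorts. It adds: "A waterfall plot will also be generated to summarise tumour size reduction graphically for the SPD of the indicator lesions identified at baseline imaging".

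On scan timing, Protocol 5.1.2.2 says "CT scan will be performed at screening, at week 13 and week 25". For patients who stop early it says "A CT scan may be performed at end of treatment if therapy terminates earlier", and Protocol 6.2.3.1 says of the end-of-treatment data "This includes a CT scan, which may be performed if it is considered clinically indicated". Protocol 4.1.4.4 sets the condition for going on: "In absence of clinical progression judged by the investigator, treatment with BI 836826 can be continued for the second course".

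On missing data, Protocol 7.4 says "No imputation will be performed on missing efficacy data". SAP 6.6 likewise leaves missing data missing unless stated otherwise.

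For best overall response, SAP 5.2.2 plans one evaluation on all investigator assessments and one on assessments with imaging. It keeps investigator-recorded PD as PD whether or not there is imaging, and adds: "For both evaluations only response assessments prior to any further NHL therapy and until PD will be taken into account". No matching sentence is written for SPD.

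**The concern.** Whether a patient has a post-baseline SPD value depends partly on how the patient did. Someone who progresses clinically during the first course does not normally start the second, so does not reach the scheduled scan. If the investigator sees no need for a CT at that point, the patient has no percentage change and no stated place in the summary or the plot. The same holds for an early death or an early switch of therapy. The patients who remain are more likely to be those who did well.

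The SAP deals with this for response but not for SPD. An early clinical progressor without a scan counts as PD in the imaging-based response evaluation, yet is absent from the waterfall plot beside it.

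At stake is how a reader judges anti-tumour activity, by dose and overall. The cohorts are small. In a Korean cohort of 3 to 6 patients, one unscanned patient is between 1/6 = 17% and 1/3 = 33% of the data. If early dropout differs between doses, the SPD comparison across doses is affected too.

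**Working it through.** **Timing of the first scheduled scan.** In the course 2 flowchart and Protocol 6.2.2.2 the CT falls at visit 9, day 36 of course 2. Course 1 lasts 49 days, so this is trial day 49 + 36 = 85. Twelve full weeks end on day 84, so day 85 opens week 13, which reproduces the stated week. The next scan, day 71 of course 3, is trial day 98 + 71 = 169, which is week 25. Protocol 3.3.2 asks only for a life expectancy of at least 3 months, about the time of the first of these scans.

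**Who can lack an SPD change.**
- Patients with a baseline lesion who leave before week 13 and have no optional or unscheduled CT.
- Patients with no indicator lesion at baseline. Protocol 3.3.2 requires measurable disease only in the expansion cohort, so escalation patients may have none. This group is not a source of outcome-related selection, but it must be counted separately from the first.

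**Denominator.** The general rule in SAP 7, which keeps patients with missing values in the denominator, is written for categorical tables. It covers the remission rate but not a continuous percentage change.

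**Possible size.** The plan gives no SPD distribution and no unscanned share, so what follows is illustration on assumed inputs.

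*Illustration A: what would be reported.* Assume that best change over all patients with a baseline lesion is Normal with mean -10% and SD 50%, floored at -100%. A share f has no scan, and every unscanned patient is worse than every scanned one.
- Observed median = -10 + 50 × z(0.5 × (1 - f)). For f = 0.2: z(0.40) = -0.253, giving -10 - 12.7 = -22.7%.
- Observed share with at least 50% shrinkage = Φ((-50 + 10)/50)/(1 - f) = Φ(-0.8)/(1 - f) = 0.212/(1 - f). For f = 0.2: 0.212/0.8 = 26.5%.

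The floor changes neither quantity.

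| Unscanned share f | Observed median | Observed share with ≥50% shrinkage |
|---|---|---|
| 0 | -10% | 21% |
| 20% | -23% | 27% |
| 30% | -29% | 30% |
| 40% | -36% | 35% |
| 50% | -44% | 42% |

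For this distribution and a given f, these are the largest possible shifts. If the scans are missing for reasons unrelated to tumour response, the expected shift is zero for any f.

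*Illustration B: the same effect from the reported side.* Assume that scanned patients are Normal with median -20% and SD 40%, and rank the unscanned share d worst.
- All-patient median = -20 + 40 × z(0.5/(1 - d)).
- All-patient share with at least 50% shrinkage = (1 - d) × Φ((-50 + 20)/40) = (1 - d) × 0.227.

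| Unscanned share d | All-patient median | All-patient share with ≥50% shrinkage |
|---|---|---|
| 0 | -20% | 23% |
| 10% | -14% | 20% |
| 20% | -7% | 18% |
| 30% | +3% | 16% |
| 40% | +19% | 14% |

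**New therapy.** The response limit in SAP 5.2.2 refers to its two response evaluations. The PFS rules there also censor at the last assessment before new therapy. The SPD text has no cut-off. Protocol 5.1.2.4 expects some patients to start next-line therapy without formal PD, and the end-of-treatment visit records other lymphoma therapy and may include a CT. A scan after new therapy could therefore supply the best change under the text as written.

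**The case against.** The other side has four fair arguments.

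First, week 13 is the first scheduled scan, not the first permitted one. Protocol 3.2 leaves additional CTs to the investigator, and a CT at early end of treatment is allowed for the very purpose of documenting progression. Some early progressors will therefore have an SPD value. A reader might infer that only patients who reach week 13 are analysed; the documents do not support that.

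Second, a reader might infer that the plan deliberately counts scans after new therapy. It does not say so; it is silent. Protocol 4.2.2.1 bars concomitant anti-neoplastic therapy, and Protocol 6.2.3.2 ends follow-up when new anti-lymphoma therapy starts, so few such scans should exist. What stands is a drafting gap.

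Third, early failures are visible elsewhere. Investigator PD counts in best overall response, the remission rate keeps patients with missing values in its denominator, PFS and FFS take in progression and death, and SPD is listed by time point. A proportion with at least 50% SPD reduction also overlaps with the remission rate, since PR requires that reduction. This limits the consequences but does not repair the SPD summary or the plot, which will be read on their own.

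Fourth, the trial is descriptive, with no formal tests (Protocol 7.2) and no key secondary endpoint (SAP 5.2.1), and some SAP text is not visible (sections 6.4 and 7.6, for example). So one can say only that the visible text has no rule for unscanned patients. This argument stands, and it sets the severity.

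**Conclusion.** The point holds in limited form. As the visible text stands, best percentage change in SPD and the waterfall plot can include only patients with a baseline and a post-baseline scan. Patients who fail early without a scan drop out with no stated accounting. The likely direction is towards more apparent shrinkage.

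The size is unknown. A reader might conclude that shrinkage is overstated by a definite amount; the documents do not support that, because they give neither the unscanned share nor the reasons for missing scans. The shifts shown (from -10% to between -23% and -44% for 20% to 50% unscanned) are upper bounds under an assumed distribution in which every unscanned patient is worse than every scanned one. They fall to zero if everyone is scanned. The remission rate is not affected in the same way.

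The missing cut-off at new NHL therapy is a smaller, separate gap. Overall severity is minor: the endpoint is secondary and descriptive, and MTD determination does not rest on it.

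**What to change.** In SAP 5.2.2 and 7.5.2:

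1. Keep the observed-case SPD summary as planned.
2. For each cohort, report the number treated, the number with a baseline indicator lesion and the number with a post-baseline SPD, with reasons for absence.
3. On the waterfall plot, mark patients who have a baseline lesion but no post-baseline scan because of progression, death or new therapy as a separate category, with no value imputed.
4. Add, as a supportive analysis, the proportion with at least 50% SPD reduction over all treated patients with a baseline indicator lesion. A median that ranks the patients in item 3 worst is optional; making it the main summary would be a matter of preference.
5. State that only scans before new NHL therapy contribute to best SPD change, in line with best overall response.

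The cost is SAP wording, a little more programming and a figure that may look less favourable. No extra scans or visits are needed.
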